1. RESEARCH BACKGROUND

Please describe the purpose of your research. Provide relevant background information and briefly state your research question(s). You may provide relevant citations as necessary. (300 Word Max.)

Despite a growing understanding that parents continue to shape adolescents' alcohol use decisions even after students leave the home and matriculate to college, parent influence remains a severely underutilized resource in the fight to curb risky drinking on college campuses—partly because, to date, parent-based interventions (PBIs) have been ineffective at reducing heavy episodic drinking (HED). Recently, we were able to develop a PBI that influenced numerous indicators of student alcohol use, including HED, by combining the informational content that characterizes a typical PBI with a live group-based social norms intervention designed to motivate parents to engage with the informational content more deeply and to really apply it to their interactions with their child. The current project aims to adapt, optimize, and extend this successful intervention in 3 key ways: (1) by employing recent advances in “co-presence” technology that will allow us to move to online delivery of the intervention without sacrificing the benefits of a live group session, (2) by conducting a year-long documentation study to expand the scope of the intervention by identifying specific parenting behaviors that are most strongly associated with reduced student risk across the first year of college, (3) by delivering the intervention across the first semester of college rather than a single session delivered during the summer, and (4) by augmenting the norms and information with engaging professional-quality video content featuring top experts on adolescent parenting.

2. SUBJECT RECRUITMENT

How will subjects be selected? What is the sex and age range of the subjects? Approximately how many subjects will be studied?

How will subjects be contacted? Who will make initial contact with subjects? Specifically, what will subjects be told in initial contact?

If subjects will be screened, describe criteria and procedures.

This study seeks to evaluate both feasibility and efficacy of the FITSTART+ app-based intervention for parents. The goal is to assess efficacy of the intervention version of the FITSTART+ app on student alcohol outcomes, relative to an active control version of the app. Participants in the clinical trial will ultimately be 400 to 600 LMU students who have a parent randomized to use either the intervention or control version of the app. The Registrar will provide student and parent contact information for the incoming freshman class (approx. 1600 students and 3000 parents). Incoming traditional, non-international first-year students (i.e., first-time college students aged 17–20 years) registered to attend LMU during the Fall semester and who have at least one parent/guardian email on file with the admissions office will be emailed an invitation to participate in a three-part web-based survey assessing experiences during their first year of college. Invitations to complete the baseline survey will be sent in July 2021 (T1) via the admissions office who will verify each student's age, year in school, and whether they have a parent/guardian email on file. The baseline survey and each follow-up survey will be open for

approximately 3 weeks. Student participants will receive a \$25 electronic gift card for completing each study survey and an additional \$10 bonus if they complete all three surveys.

To participate in the study, students must:

- 1) Be a first-year college student 17–20 years of age.
- 2) Have a parent/guardian email on file with the admissions office.
- 3) Be a domestic (i.e., non-international) student.
- 4) Consent to participate (with parental consent for minors under age 18).

3. PROCEDURES

Summarize fully all procedures to be conducted with human subjects.

This intervention study tests the feasibility of the FITSTART+ program and evaluates the effects of the parent-program on student drinking. That is, the program will be delivered to parents exactly as it might be delivered in the real world, out of the study context (no incentives, knowledge of condition assignment, or awareness of associated student survey study). Simultaneously, alcohol use outcomes will be assessed among the first-year students of participating parents with students incentivized to complete 3 surveys spanning their first year. Recruitment will begin in July 2021 prior to matriculation and will be identical to the IRB approved recruitment procedure in our successful previous R21 FITSTART project (LMU IRB 2014 SP 45). In early summer, the Registrar will provide the research team with new student and parent contact information.

Emails sent by the university's admissions office will only invite students who meet our eligibility criteria to participate in a 3-part longitudinal survey study about their transition into college life. These invitations will mention that they will receive \$25 for each 15-minute survey and an additional \$10 bonus if they complete all three (for a total of \$85). This email will contain a link for interested students to complete the IRB-approved informed consent form. When consenting, students indicate whether they are 18 years of age or older, or under 18. Students 18 or older will provide consent while those under the age of 18 who wish to participate will provide assent and then will be asked for their parent's email address and their parents will be sent a consent form (Consent Appendix). As part of the consent form, students will also agree to the potential linking of their data with data provided by their parent(s) who may also be participating in a separate study. The form will specify that their survey responses will NOT be shared with their parents under any circumstances and their participation in the study will be confidential. If students agree to the potential parent-data linkage, they will immediately be redirected (triggered automatically by Qualtrics) to begin the baseline survey. Incoming first-year student recruitment will continue until 700 students have completed the baseline survey.

All parents of students who complete the baseline survey will be invited via email to take part in the FITSTART+ program. To sign up, parents will need to click a link in the email to visit the FITSTART+ landing page which will include a general description of the application (no information about alcohol), a description of the parenting experts featured in the application, and a parent verification form. The verification form, which will be a Qualtrics survey embedded in the landing page, will serve two important purposes: it will (1) match parents to their students in the dataset; and (2) randomize parents to the treatment or control version of the app. The randomizer will be set up in Qualtrics to balance assignment to an app condition by students' birth sex. At the end of the verification form, parents will receive a web URL linking to the sign-up page for the application to which they were randomized. Parents who click the link will be prompted to create their user account. In order to not artificially bias parents' app use, parents will be unaware that there is more than one version of the app, they will not be incentivized to use the app, and they will not be told that their child is participating in a survey study.

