12. RANDOMIZATION

Describe criteria for assigning subjects to sub-groups such as "control" and "experimental."

Although the participants among whom outcomes will be assessed are students, parents of these students will be the ones randomized to the treatment or control version of the app. A verification form on the informational FITSTART+ landing page, will serve two important purposes: (1) it will match parents to their students in the dataset; and (2) randomize parents to the treatment or control version of the app. The randomizer will be set up in Qualtrics to balance assignment to an app condition by students' birth sex. At the end of the verification form, parents will receive a web URL linking to the sign-up page for the application to which they were randomized. The treatment condition will receive the FITSTART+ intervention while the control group will receive a similar program which covers all non-alcohol related resources included in the intervention version of FITSTART+ (e.g., general parenting information, university-specific resources).

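### Parents are said to be unaware of the student survey, yet a parent of each 17-year-old is sent a consent form for it, so the real-world feasibility claim does not hold for those families

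*Protocol*

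**What the plan says.** Protocol section 3 (Procedures) opens with two aims: "This intervention study tests the feasibility of the FITSTART+ program and evaluates the effects of the parent-program on student drinking". It goes straight on to explain that "the program will be delivered to parents exactly as it might be delivered in the real world, out of the study context", and spells this out in a parenthesis: "no incentives, knowledge of condition assignment, or awareness of associated student survey study". Later in the section, the sentence that begins "In order to not artificially bias parents' app use" lists what parents will not know and ends with the statement that "they will not be told that their child is participating in a survey study". Neither statement carries an exception.

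Protocol section 2 (Subject Recruitment) admits students aged 17 to 20 and makes parental consent an eligibility condition for those under 18. Section 3 gives the mechanics. A student under 18 assents and supplies a parent's email address, and "their parents will be sent a consent form". Every parent of a student who completes baseline is then invited to the app.

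On allocation, section 12 (Randomization) says: "The randomizer will be set up in Qualtrics to balance assignment to an app condition by students' birth sex". No other balancing factor is named. The SAP models all students together and plans no analysis by minor status or parental awareness.

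**The concern.** The protocol presents parental unawareness as a property of the design and ties it to unbiased app use. Its own consent procedure removes that property for an identifiable group. A parent who has consented to a child's survey knows that the child is being studied when deciding whether to sign up and how much to use the app. There is also a selection step: a 17-year-old is eligible only if a parent has answered a study request, and such parents may respond differently to the app invitation that follows.

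What is at stake is the feasibility aim. If sign-up and app use are reported as one figure and described as what would happen outside a study, the description is wrong for part of the sample. Nobody could tell from the pooled figure how much that part contributed.

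**Working it through.** The plan states no figure on this point, so there is none to reproduce. The check compares passages and then sizes the group.

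**1. Order of events for a 17-year-old (Protocol sections 2 and 3).** Recruitment starts in July 2021. The student assents and gives a parent's email address; the parent is sent the consent form; the student completes baseline; all parents are invited to the app; the sign-up form randomizes. The form is thus sent before the app invitation, and parental consent is a condition of eligibility.

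**2. Is there an exemption?** None was found. The two unawareness statements in section 3 are unqualified, and the app invitation covers all parents of baseline completers.

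**3. Does a narrow reading rescue the text?** One could take it to mean only that the app invitation does not mention the survey. The parenthesis in section 3 rules out awareness as such, which is wider than silence in one email.

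**4. Does it bias the arm comparison?** Whether a form is sent depends on the student's age at consent, which is fixed before randomization and unrelated to the arm. The expected share of aware families is therefore the same in both arms. The SAP (Additional Model Considerations) also tests baseline equivalence on demographic variables and adjusts for any associated with assignment, which would cover a detected chance imbalance in age.

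**5. Number affected.** Let p be the share aged 17 at consent. The documents do not give it; 10% to 40% is assumed.

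| p | of 400 trial students | of 600 trial students | of 700 baseline completers |
|---|---|---|---|
| 0.10 | 40 | 60 | 70 |
| 0.20 | 80 | 120 | 140 |
| 0.40 | 160 | 240 | 280 |

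**6. Possible shift in a pooled uptake figure.** If uptake is u in families of adult students and u + x in families of minors, pooled uptake is (1 − p)u + p(u + x) = u + px. The shift is px. With x assumed at 5 to 20 percentage points:

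- p = 0.10: 0.10 × 5 = 0.5 to 0.10 × 20 = 2 points
- p = 0.40: 0.40 × 5 = 2 to 0.40 × 20 = 8 points

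Both p and x are assumptions, and x could also be negative. For scale, the targets of 400 to 600 trial students from 700 baseline completers imply that 400/700 = 57% to 600/700 = 86% of students have a parent randomized.

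**The case against.** The strongest reply is that this is a wording slip with little consequence. Several parts of that reply stand.

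- Parents of minors still receive the same invitation and app, get no incentive, and do not know that there are two versions. Only knowledge of a survey differs, and knowing of a survey is not knowing that the app is evaluated through it.
- The form goes to the address the student gives, while all parents are invited. In two-parent families the app user may not be the parent who consented.
- Under-18 status is already recorded at consent, and 17 is a separate age category in the survey, so the group can be separated at any time.
- The SAP contains no feasibility analysis, so a pooled uptake figure is implied by the protocol's aim and is not a specified result.
- Families of 17-year-olds belong to the target population. Dropping them from the main uptake figure could make it less representative.

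A reader might go further and infer that the efficacy result is compromised: that alerted control parents raise alcohol with their child, that minors under-report drinking, or that the effect is diluted. With 40% minors and the whole effect lost among them, the SAP's d = .20 would become .20 × (1 − 0.40) = .12. The documents do not support this. The parental form is not available, so whether it mentions alcohol or data linkage cannot be checked. Students are assured that parents will not see their answers. The loss of effect is a pure assumption, and its direction is open: if awareness raises app use, the effect in these families could be larger.

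None of this removes the contradiction. Two unqualified statements in section 3 are untrue for every family in which a minor was properly enrolled.

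**Conclusion.** The protocol claims a delivery condition that its own consent procedure breaks for families of 17-year-olds. The secure consequence is limited to feasibility: pooled sign-up and app-use figures mix study-aware and study-unaware families, and the real-world description does not hold for the first group.

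The size is unknown because the age distribution is not given. At an assumed 10% to 40% aged 17, it is 40 to 240 of 400 to 600 students, and a shift in pooled uptake of 0.5 to 8 points if awareness adds 5 to 20 points. The comparison of intervention with control should not be read as biased on this account. Any influence on the size of the effect is unknown in amount and direction.

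**What to change.** 1. In Protocol section 3, limit both unawareness statements to parents of students aged 18 or over, and say that a parent of each younger student will know of the survey through the consent form.
2. Use the under-18 status recorded at consent to report sign-up, account creation and app use for all parents and separately by minor status. Keep the all-parent figure, and reserve the real-world, study-unaware description for the 18-or-over group.
3. Name in the SAP one sensitivity analysis that repeats the treatment-by-time contrasts in students aged 18 or over, with the primary model unchanged.

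Balancing the randomizer on minor status is optional. Parental consent for minors stays as it is.

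The cost is a few sentences, since the flag is already collected, and some precision. With the same variance and a share p excluded, standard errors grow by about 1/√(1 − p): 1/√0.90 = 1.05 at 10% and 1/√0.60 = 1.29 at 40%. The sensitivity analysis should therefore be read for whether the estimate moves, not for whether it reaches significance.

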4. RISKS / BENEFITS

What are the potential benefits to subjects and/or to others?

What are the reasonably foreseeable risks to the subjects? (Risks may include discomfort, embarrassment, nervousness, invasion of privacy, etc.) If there are potential risks to subjects, how will they be minimized in advance? How will problems be handled if they occur?

A. Potential Risks

Psychological risks posed by the research are primarily related to the sensitivity of some of the measures. Student participants will complete measures assessing alcohol-related beliefs and behaviors that may be private. These questions may make subjects uncomfortable or be perceived as an intrusion on their privacy. They also will be asked to report on potentially illegal behaviors, such as drinking under the legal age. Answers to these questions could pose a risk if the information were known and linked to identifiable individuals. To mitigate risks participants will be reminded that they are free to skip any questions that make them feel uncomfortable. Additionally, their responses will not be directly linked to any identifiable information.

B. Potential Benefits

The proposed study will evaluate the efficacy of a parent-based normative feedback intervention that aims to leverage parental influence to reduce the risk for heavy drinking and associated consequences among incoming first-year college students. Parents in the intervention group will learn about the risks of alcohol use among students and discuss strategies to maintain an open dialogue with their child regarding alcohol-related attitudes and expectations. It is anticipated that parents and students in the intervention condition will gain substantial benefit from participating in the study, with regard to parents learning about alcohol risk and communication, and students engaging in less risky alcohol use behaviors and negative alcohol-related consequences. In addition, all student participants in both the intervention and control groups will be monitored for high-risk drinking levels and endorsement of high levels of negative consequences, and will be provided appropriate referrals when necessary. Specifically, participants reporting consumption of potentially lethal doses of alcohol (BAC's above .30) or RAPI consequences scores (incidence) of 16 or above on the initial or any follow-up questionnaire will be contacted and informed of their risk, and provided referrals for clinical services. This is a benefit that would not otherwise occur without study participation.

5. CONFIDENTIALITY

Will subjects be identifiable by name or other means? If subjects will be identifiable, explain the procedures that will be used for collecting, processing, and storing data. Who will have access to data? What will be done with the data when the study is completed? If you are collecting visual images of your subjects please justify this.

Parent/student dyads will be set up in order to link the data. To do this the parents and the students will share the same PIN. If more than one parent decides to participate their PINs will end in either -1 or -2. The sharing of PINs allows for the linkage of data without individuating information attached. This linkage is solely for analytic purposes and will only be used to look at student outcome data.

To maintain confidentiality of data submitted over the internet, participants will submit all information via Qualtrics (Qualtrics has SAS 70 Certification and meets the rigorous privacy standards imposed on health care records by the Health Insurance Portability and

Accountability Act). All Qualtrics accounts are hidden behind passwords and all data is protected with real-time data replication. Data transfer will be protected using a Secure Socket Layer with 128-bit encryption. This is the same level of encryption used for most banking transactions and offers the highest degree of protection available for data transfer. The server is physically located in a secure, commercially protected co-location facility with 24-hour locked and monitored keycard access, within a locked room, within a locked server rack, with a locking face-plate protecting the server itself from physical access without authorization. Electronic protection is provided by a commercial-grade firewall, with continuous monitoring of the server for any attempts at electronic invasion. Any associated paper documents will be stored in a locked file cabinet within the lab. Study results will be reported in aggregate, so that individual participants will not be identifiable in any research reports or presentations of the proposed study. As we often receive requests for our data to be used in meta-analyses, data from the study will be kept for 5 years after the completion of the project. After this period of time all data will be destroyed.

6. INFORMED CONSENT

Attach an informed consent form or a written request for waiver of an informed consent form. Include waiver of written consent if appropriate. If your research is being conducted in another language, please include copies of the translated "Informed Consent" or "Waiver of Written Consent" forms.

Please see attached CONSENT APPENDIX for consent forms.

7. STUDENT RESEARCH

When a student acts as principal investigator, a faculty sponsor signature is required on the application form.

N/A

8. RENEWAL APPLICATIONS

When the submission is a Renewal Application, include a summary of the research activities during the previous granting period specifically addressing: number of subjects studied and any adverse reactions encountered, benefits which have been derived, any difficulty in obtaining subjects or in obtaining informed consent, and approximate number of subjects required to complete the study.

N/A

9. PAYMENTS

If subjects are to be paid in cash, services, or benefits, include the specific amount, degree, and basis of remuneration.

Students will receive a \$25 gift card for each 15-minute survey and an additional \$10 gift card bonus if they complete all three (for a total of \$85). Gift cards will be sent to students via email within 48 hours of survey completion via an online gift card service called giftbit (www.giftbit.com).

10. PSYCHOLOGY SUBJECT POOL

When students from the Psychology Subject Pool (PSP) are to be involved as subjects, permission must be obtained from the PSP prior to running subjects.

Forms are available from the Psychology Office in [name]. It is not necessary to inform the IRB of approval from the PSP, however the PSP requires IRB approval prior to permission for using the pool being granted.

N/A

11. QUALIFICATIONS AND TRAINING

Describe the qualifications of, or method of training and supervision afforded student experimenters. This includes past experience, type and frequency of student/sponsor interactions during the experiment, and Human Subjects Protections Training.

All experimenters have completed the NIH or CITI Protection of Human Subjects training course. We have attached copies of each researcher's certificate.

12. RANDOMIZATION

Describe criteria for assigning subjects to sub-groups such as "control" and "experimental."

Although the participants among whom outcomes will be assessed are students, parents of these students will be the ones randomized to the treatment or control version of the app. A verification form on the informational FITSTART+ landing page, will serve two important purposes: (1) it will match parents to their students in the dataset; and (2) randomize parents to the treatment or control version of the app. The randomizer will be set up in Qualtrics to balance assignment to an app condition by students' birth sex. At the end of the verification form, parents will receive a web URL linking to the sign-up page for the application to which they were randomized. The treatment condition will receive the FITSTART+ intervention while the control group will receive a similar program which covers all non-alcohol related resources included in the intervention version of FITSTART+ (e.g., general parenting information, university-specific resources).

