PRS Cover Page for Statistical Analysis Plan

Title: Parent Feedback Intervention Targeting Student Transitions and Alcohol Related Trajectories (+) Efficacy Study (FITSTART+)

Date: April 26, 2021

ClinicalTrials.gov Identifier: NCT04549454

Statistical Analysis Plan

Examines the efficacy of FITSTART+. Main effects of the intervention will be examined with hierarchical generalized linear models (HGLM) using SAS. HGLM permits the simultaneous examination of relationships among variables at different levels, for example variables measured over assessment periods assumed to fluctuate within an individual (e.g., student drinking behavior) with variables considered to have stable characteristics (i.e., parent intervention condition). Using this framework, time will be specified as a Level 1 varying predictor nested within individuals (Level 2). The following model will be used to determine main effects of the intervention conditions compared to control:

$$\text{Level 1: } DV_{ti} = \pi_{0i} + \pi_{1i}(T1)_{ti} + \pi_{2i}(T2)_{ti} + \varepsilon_{ti}$$

$$\text{Level 2: } \pi_{0i} = \beta_{00} + \beta_{01}(Tx)_i + r_{00i}$$

$$\pi_{1i} = \beta_{10} + \beta_{11}(Tx) \quad t \text{ indexes repeated measure} \quad \pi_{2i} = \beta_{20} + \beta_{21}(Tx) \quad i \text{ indexes individuals}$$

Respective model DVs will include total drinks per week from the DDQ, consequence composite score, and number of HED episodes during the past month. T1 and T2 will be dummy coded time variables (T1 = student baseline [coded 0] to 1 month into college follow-up [coded 1], T2 = student baseline [coded 0] to 6 months into college follow-up [coded 1]). Tx will be a categorical predictor comparing the intervention condition [coded 1] to control [coded 0]. With this model, intercept treatment differences will represent treatment differences at baseline (e.g., group differences in student drinking at baseline) and slope differences will represent changes over time (e.g., did students of intervention parents reduce their drinking between baseline and follow-up assessments more than students of control parents?). The intercept includes a random effect, which will model the subject-specific heterogeneity in the outcome and control for correlated data due to individuals. Pairwise comparisons (post hoc Tukey's) were conducted to examine mean differences between conditions at each time point.

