Missing data. Attrition bias will be tested by evaluating whether baseline outcomes differ between student and parent dropouts versus completers. HGLM is optimal in that it allows for unbalanced data, giving heavier weights to participants with more non-missing values. HGLM also assumes that missing values are missing at random as opposed to non-ignorable. The pattern-mixture approach to non-ignorable missing data will be used to assess the sensitivity of findings to the presence of missing data. If the pattern of missingness appears to pose a threat to the validity of the experimental manipulation (i.e., student attrition is related to parent random assignment, or the predictors of attrition are different for students of intervention vs control parents), more powerful missing techniques will be used, such as multiple imputation.

Additional Model Considerations. Student outcomes (drinks per week, HED frequency, and negative consequences) are count variables, which can have skewed distributions when the overall mean is low. Alternative models could also specify a Poisson or Gaussian distribution for the Level 1 errors. We will consider whether the

Level 1 components are more appropriately modeled as Gaussian or Poisson. Further, in spite of randomization at the parent level, we will conduct baseline equivalence tests between the FITSTART+ student participants to establish successful parent randomization effectiveness, including pre-treatment alcohol use, negative consequences, and demographic variables. Any student variables that are associated with treatment assignment, in spite of parent randomization, will be included as covariates.

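### The plan does not say whether the arm is drawn per parent or per student, so Tx may be undefined for a student with two enrolled parents

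*Protocol*

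**What the plan says.** Four statements meet here.

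- **Who is invited.** Protocol section 3: "All parents of students who complete the baseline survey will be invited via email to take part in the FITSTART+ program". Section 2 puts the incoming class at about 1600 students and 3000 parents.
- **Two parents are foreseen.** Protocol section 5: "If more than one parent decides to participate their PINs will end in either -1 or -2". That section deals with linking data and does not mention the arm.
- **What is randomized.** Protocol section 12: "parents of these students will be the ones randomized to the treatment or control version of the app". Sections 3 and 12 both give the verification form two jobs, matching the parent to a student and randomizing. The only constraint stated is balance on the student's birth sex. The SAP, under Additional Model Considerations, also places the draw with the parent: "in spite of randomization at the parent level, we will conduct baseline equivalence tests".
- **What is analysed.** The SAP model nests time within the individual student and has one treatment term: "Tx will be a categorical predictor comparing the intervention condition [coded 1] to control [coded 0". There is no parent or family level.

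Several passages suggest that one arm per student is meant. Section 2 speaks of "400 to 600 LMU students who have a parent randomized to use either the intervention or control version of the app", in the singular. Section 5 says "Parent/student dyads will be set up in order to link the data". The SAP counts condition among "variables considered to have stable characteristics (i.e., parent intervention condition", and its power paragraph assumes randomization of persons. None of these says what happens when a second parent of the same student reaches the form.

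**The concern.** The unit that is randomized (the parent) is not the unit on which outcomes are measured (the student), and the plan allows two of the first for one of the second. In that situation a rule is needed to carry the arm from parent to student, and none is written. A form built to randomize whoever verifies would give some families one parent in each arm.

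Three things would follow. The contrast would be diluted, because some control students would have a treated parent and some treated students an untreated one. The analyst would have to choose a coding of Tx that was not pre-specified. And section 3's wish that parents not know of a second app version would be harder to keep, since two parents of one student could compare an app with alcohol content and one without. The mixed exposure itself cannot be repaired at analysis.

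**Working it through.** **Plan's own figure.** The SAP's power paragraph states 300 per arm and describes power as excellent, without a number. There is nothing to reproduce, and the point does not depend on it.

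**Step 1: share with mixed arms.** Suppose each parent is drawn separately, 1:1 and independently. The four outcomes for two parents are equally likely and two of them are mixed. So half of the two-parent students are mixed, or f/2 of all enrolled students.

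**Step 2: plausible values of f.** The documents do not give f. As an illustration, assume that every student has one or two parents on file and that parents sign up independently with probability p.

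- 3000/1600 = 1.875 parents per student, so 87.5% have two and 12.5% have one.
- Share of students with at least one enrolled parent: S = .875[1 − (1 − p)²] + .125p.
- f = .875p²/S.
- Section 3 recruits 700 baseline students and section 2 expects 400 to 600 in the trial.

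| Enrolled | S | p | f | Mixed students |
|---|---|---|---|---|
| 400 of 700 | .571 | .368 | .207 | 400 × .207/2 = 41 |
| 600 of 700 | .857 | .661 | .446 | 600 × .446/2 = 134 |

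A low value, f = .05, is added as a separate assumption. It gives 400 × .05/2 = 10 to 600 × .05/2 = 15 mixed students.

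**Step 3: dilution under first-parent coding.** Let d be the effect when all of a student's enrolled parents are treated, taken as equal for one- and two-parent students. Let kd be the effect when one of two is treated.

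- One-parent students: difference d.
- Two-parent students, first parent treated: .5d + .5kd.
- Two-parent students, first parent control: .5kd + .5 × 0.
- Difference among two-parent students: .5d, whatever k is.
- Overall: (1 − f)d + f(.5d) = d(1 − f/2).

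With d = .20:

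- f = .05: .20 × .975 = .195
- f = .207: .20 × .896 = .179
- f = .446: .20 × .777 = .155

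**Step 4: the coding chosen matters.** Take 600 students, f = .25, 20% attrition, d = .20, and the full effect from one treated parent. Use a simple two-sample comparison with SD 1 and two-sided alpha .05 (both assumed). With no mixed arms this gives power .59 at 240 per arm. The SAP's longitudinal calculation rests on variance inputs that it does not report, so these figures serve only to compare the codings.

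- Drop mixed students: 600 × .875/2 × .8 = 210 per arm, power .54.
- First parent's arm: d = .20 × .875 = .175, power .48.
- Any treated parent sets Tx = 1: 270 against 210 students, power .585. But two-parent families then make up .1875/.5625 = 33% of Tx = 1 and .0625/.4375 = 14% of Tx = 0, so the groups are no longer comparable as randomized.

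**The case against.** The strongest reply is that the protocol does not describe a separate draw for each parent. A reader might infer from section 12 that it does, and hence that mixed families are built into the design. The text does not support that. It says in the plural that parents are randomized, by a form that also matches them to their student and balances on a student characteristic. A form that looks up the student and returns an arm already assigned fits this wording equally well. The form itself is not reproduced, and nothing shows that it lacks such a rule or that any family received mixed arms. The remedy may turn out to be a sentence.

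The sizes are also open to challenge:

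- f is assumed throughout. The contact counts are approximate and describe the whole class, not the 700 baseline students.
- f = .05 does not come from the independent sign-up model at 400 to 600 students. Solving .875p/(1.875 − .875p) = .05 gives p = .102 and S = .182, or about 128 of 700 students. It stands for the case where second parents rarely join.
- f = .45 needs 66% sign-up from parents who receive no incentive.
- If the two parents' effects add, first-parent coding gives .5(2d + d) − .5(d + 0) = d among two-parent students. That is no loss against any effect the plan states.
- Coding any treated parent as Tx = 1 costs little power, though it gives up the randomized comparison unless the number of enrolled parents is handled.

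All of this limits the claim but does not remove the gap. Two enrolled parents are expressly foreseen, the unit of the draw is not stated, and the SAP gives no Tx for parents in different arms.

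**Conclusion.** The point holds as a gap in the written plan and should be fixed. The documents leave open whether the draw is per parent or per matched student. Only under a per-parent draw would about half of the two-parent students be mixed, with Tx undefined for them.

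In that case first-parent coding would still be a valid intention-to-treat contrast, but smaller by the factor 1 − f/2: 2.5% at f = .05, about 10% at f = .21 and about 22% at f = .45. These figures assume independent 1:1 draws and the same effect of treating all enrolled parents whether one or two enrol. If few second parents join, the loss is small.

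The case for acting therefore rests less on the upper figures than on two facts: mixed arms cannot be undone once allocated, and the coding of Tx would be chosen after the event. The documents do not support saying that mixed allocation is specified or that it happened.

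**What to change.** - Draw the arm once per student, identified by the shared PIN and balanced on birth sex, when the first parent verifies.
- Have the form return that same arm to any later parent of the student.
- State this in protocol sections 3 and 12.
- In the SAP, define Tx as the student's assigned arm.

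This matches the person-level randomization assumed in the SAP's power paragraph. The cost is a small change to the form so that it stores and retrieves the arm by PIN, plus a sentence in each of the three places. No extra participants are needed. The documents do not say whether the form can already do this; if it does, only the text has to be added.
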